5.3.4 Definition of non-compliant population, and analysis and management of missing data

All data will be monitored by an independent data monitoring committee consisting of surgical experts, epidemiologists, RCT experts, statisticians and surgeons.

5.3.5 Statistical analyses

All statistical analyses will be performed with a two-sided significance level of 0.05 and conducted using SAS software, version 9.4 (SAS Institute).

VI. Quality of life questionnaire

6.1 Patient-reported clinical outcome assessment scale PRO 147 (V1.0) for Cervical Cancer

The research team developed its own scale assessment related to patient reported outcomes in cervical cancer, which is based on the patient's perspective to assess the outcome after surgery. Cervical cancer is the fourth most common cancer in women, and its incidence has been on the rise in recent years, especially in younger patients. Since the uterus is located in the central pelvis, damage to pelvic floor tissues by surgery may cause a variety of complications such as urinary, intestinal, vaginal and lower limb dysfunction, which cannot be accurately assessed by conventional scales. Considering the high survival rate of patients with early-stage cervical cancer, it is especially important to study the short-term and long-term treatment effects for patients.

According to the U.S. Food and Drug Administration (FDA), patient reported outcome (PRO), a measure of any aspect of a patient's health status that comes directly from the patient, is a valid patient-centered, multifaceted means of evaluating treatment outcomes (such as symptom improvement or related function) that is widely used in clinical practice and trials.

The research team has developed the Patient-reported Clinical Outcome Assessment Scale PRO 147 (V 1.0) for cervical cancer based on this concept. This scale is based on three domains including daily life, psychological and social life, with 147 questions covering 13 latitudes: urinary dysfunction (URI), bowel dysfunction (BOW), pelvic organ prolapse (POP), loss of ovarian function (OVA), lymphatic dysfunction (LYM), neurological dysfunction (NEU), sexual dysfunction (SEX), anxiety (ANX) depression (DEP), stigma (SHA), life beliefs (BEL), social support (SUP), and daily life (LIF) to assess patient prognosis. At present, our scale has been screened, and completed the expert review, and now is in the pilot study phase. So far, there are about 100 patients have completed the survey, and the information is very useful for future complication management and surgical efficacy assessment.

6.2 Generic quality of life questionnaire

Other selected quality of life questionnaires relate to postoperative symptoms (e.g., pain) as well as disease-specific and general health-related quality of life. These surveys are self-administrated and provide an understanding of the patient's quality of life, and will take less than 30 minutes to complete.

The current scale used for study follow-up is mainly the EORTC Quality of Life Measurement Scale QLQC30 (V3.0) scale, which is intended for most oncology patients and is a universal scale. From a systematic review including 156 studies, Casper Tax et al. found that the European Organization for Research and Treatment of Cancer, Quality of Life Questionnaire, Cervical Cancer Module (EORTC QLQ-CX24) and the Functional Assessment of Cancer Therapy for Cervical Cancer (FACT-Cx) are the only cervical cancer-specific instruments to date. EORTC-QLQ-CX24 appears to be the most commonly used instrument to assess Health Related Quality of Life (HRQoL) in patients with cervical cancer, and the developers of the EORTC QLQ-CX24 proposed in their study that no test-retest analysis was performed and response over time. Both scales are simple and universal, but can only distinguish between patients with early versus advanced disease and those who are receiving versus not receiving treatment. However, whether the efficacy of different treatments (e.g., surgery versus chemotherapy) or different surgical approaches (e.g., laparoscopic radical hysterectomy versus abdominal radical hysterectomy) can be distinguished has not been reported. It indicates that EORTC-QLQ-CX24 has some limitations in the evaluation of efficacy.

VII. Methods of Data Monitoring

7.1 Study monitoring

7.1.1 Trial Safety Committee

An independent Trial Safety Committee (TSC) will be established to review the safety and efficacy data collected during the study. The TSC will be composed of individuals who are independent of the study and not directly or indirectly involved in the

administration of the study. Members will include the following individuals.

Two gynecologic oncologists not involved the trial.

Two statisticians not involved in the trial.

Members of the Gynecologic Oncology Committee (Shanghai Medical Association Obstetrics and Gynecology Section, Shanghai Physicians Association Obstetrics and Gynecology Section)

7.1.2 Trial Management Committee

A Trial Management Committee (TMC) will be established for this study to review and oversee data and analysis. The TMC will be composed of the main center study leader, the sub-center leaders, and the study statistician, and will not have a conflict of interest with the funding provider. The management committee will meet every four months, and after each meeting, the committee will recommend that the study continue according to the protocol or recommend modifications to the protocol based on the results of the data review.

7.1.3 Data Monitoring Committee

A Data Monitoring Committee (DMC) will be established to independently review and oversee data and analysis. The DMC does not have a conflict of interest with the funding agency.

7.2 Interim Analysis

The ethics committee has the right to terminate the study when the number of deaths reaches a critical level or when the difference in progression-free survival or overall survival between the two groups is significant; the ethics committee has the right to terminate the study when there is a violation of ethics during the progress. To ensure the compliance of the patients, participants in this study will be given priority for treatment at our hospital, and there will be dedicated staff for post follow-up and data collection.

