3.12 Sample size

This study uses a non-inferiority trial design, and the primary outcome is the rate of OS at 5 years. The sample size is calculated based on the difference between the two groups of 5-year OS rate. The 5-year OS rate of the patients in the open surgery group is estimated to be 72% based on the previous clinical data from our hospital.

Based on the assumptions of (i) the 5-year OS rate of 72% in the open surgery group, (ii) a non-inferiority margin of 8%, (iii) 80% power, and (iv) a one-sided alpha of 0.025, the sample size estimation resulted in 495 subjects per group (calculated with SAS software, version 9.4). Considering a 10% drop-out rate and the randomization scheme with block size of 6, a total of 1104 subjects should be randomized (552 per group).

3.13 Recruitment methods:

The study team centers will advertise this study at their cervical cancer clinic. If the patients are interested, they will be further introduced in detail about the study background, randomization and surgical procedures, and the patients can voluntarily choose whether to participate in the trial. After patients sign the informed consent forms, members of the study team will review their eligibility according to the inclusion and exclusion criteria. Patients will then be randomized to receive either of the surgical

procedures. Finally, the patients will be followed up according to the follow-up schedule.

IV. Allocation, Blinding and Unblinding

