5.3.3 Secondary outcome analysis

a) The rate of PFS at 5 years:

Cox proportional hazards model will be used to estimate the hazard ratio and 95% CI for the effect of treatment on the 5-year PFS rate.

b) Analysis of continuous outcomes:

The continuous outcomes include operative duration, anesthesia time, blood loss during operation, postoperative pain score and postoperative hospital stay. The outcomes with normal distribution will be summarised using mean and standard deviation (SD), while the outcomes with non-normal distribution will be summarised using median and interquartile. The differences in the outcomes and 95% CIs will be analysed by generalised linear model (GLM) with treatment as fixed effect and with normal distribution and identity link function.

c) Analysis of binary outcomes:

The intraoperative complications, postoperative complications, one-month and one-year postoperative quality of life and sexual life will be treated as binary outcomes, and will

be summarised by number (%) of participants with the event. The differences in the outcomes and 95% CIs will be analysed by GLM with treatment as fixed effect and with binomial distribution and identity link function.

d) Interim analysis

The O'Brien Fleming method will be used to conduct an interim analysis three years after the study. If the study has conducted only once interim analysis, the α level will be set as 0.048 in the final analysis.

4. Safety analysis

Adverse events (AEs) will be summarised using the number of AEs, the number (%) of participants with AEs by groups.

5. All analyses will be performed with a two-sided significance level of 0.05 and conducted using SAS software, version 9.4 (SAS Institute).

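### Section 7.2 allows a stop on an undefined significant PFS or OS difference, with no link to the O'Brien-Fleming interim look in 5.3.3 d) or to the independent committees

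*Combined protocol and SAP*

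**What the plan says.** Two sections of the combined protocol and SAP deal with interim stopping.

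- **Section 5.3.3 d)**: "The O'Brien Fleming method will be used to conduct an interim analysis three years after the study". If only one interim analysis has been done, the α "level will be set as 0.048 in the final analysis". The endpoint, information fraction, interim boundary and acting body are not given.
- **Section 7.2 (Interim Analysis)**: the ethics committee may end the trial on either of two outcome triggers. One is a death count at some critical point, which is left undefined. The other applies "when the difference in progression-free survival or overall survival between the two groups is significant". For this survival comparison there is no level, boundary, direction, timing or number of looks, and O'Brien-Fleming is not mentioned. A further clause lets the same committee stop the trial for breaches of ethics.

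The only general level is in 5.3.5 (also stated in 5.3.3): "All statistical analyses will be performed with a two-sided significance level of 0.05". The sample size in 3.12 uses "a one-sided alpha of 0.025".

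The independent bodies are described elsewhere. The TSC is set up "to review the safety and efficacy data collected during the study" (7.1.1), and the DMC reviews data and analyses (7.1.3). Section 7.2 gives neither a part in the stopping decision.

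**The concern.** Section 5.3.3 d) controls error by making the interim criterion very strict. Section 7.2 then states a second statistical criterion under the same subject heading, adds PFS as a trigger, and attaches no error control. Someone carrying out the plan cannot tell which criterion decides whether the trial stops. If 7.2 is followed at the general 0.05 level, an early stop by chance becomes much easier than the O'Brien-Fleming plan allows.

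At stake is the answer to the primary question. The trial randomizes 1104 patients, at 80% power, to compare 5-year OS. A stop on a chance difference would come before 5-year OS can be estimated properly in either arm.

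**Working it through.** **Inputs from the documents.** One interim look and a final level of 0.048 (5.3.3 d); general two-sided level 0.05 (5.3.5); 5-year OS 72%, margin 8 points, 1104 patients (3.12); three-year enrolment (2.1 under Qualification criteria).

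**Assumptions, because the documents give no figures.** Information fraction t at the look; correlation ρ between the OS and PFS test statistics; differences counted in either direction.

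**1. Reproduce the 0.048.** For a two-look O'Brien-Fleming design with overall two-sided 0.05, find C such that P(|Z₁| > C/√t or |Z₂| > C) = 0.05, with corr(Z₁, Z₂) = √t. At t = 0.5, C = 1.977.
- Interim: 1.977/√0.5 gives |Z| > 2.797, p = 0.0052.
- Final: |Z| > 1.977, p = 0.0480, which matches the plan.

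So 0.048 corresponds to one look, on one endpoint, at p of about 0.005.

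**2. Chance of meeting the 7.2 criterion with equal arms, one look at 0.05.**
- OS alone: 0.050, and 0.050/0.0052 is about 10 times the O'Brien-Fleming figure.
- OS or PFS, P(|Z_OS| > 1.96 or |Z_PFS| > 1.96) from the bivariate normal: 0.070 at ρ = 0.9, 0.084 at ρ = 0.7, 0.091 at ρ = 0.5. This is about 14 to 18 times 0.0052.
- Upper limit at ρ = 0: 1 − 0.95² = 0.0975.

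If only harm counts, the OS-alone figures both halve (2.5% against 0.26%) and the ratio is unchanged.

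**3. Same calculation if the O'Brien-Fleming boundary applies to both endpoints (|Z| > 2.797).** 0.0079 at ρ = 0.9 to 0.0099 at ρ = 0.5, and at most 0.0103 at ρ = 0. Against 0.0052 this is about 1.5 to 2 times.

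**4. Where year 3 falls.** Assume uniform accrual over 3 years, exponential survival with λ = −ln(0.72)/5 = 0.0657 per year, and no dropout.
- Deaths by year 3: 1104 × [1 − (1 − e^(−3λ))/(3λ)], about 102.
- Total deaths: about 225 if the data close at year 5; 1104 × 0.28 = 309 if each patient is followed for exactly 5 years; about 383 if all are followed to year 8.
- t is therefore 102/225 = 0.45, 102/309 = 0.33 or 102/383 = 0.27.
- The O'Brien-Fleming interim p is 0.0033 at t = 0.45 and 0.0006 at t = 0.33, so the gap to 0.05 would be wider than in step 2.

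**5. Is the non-inferiority error raised?** At the margin OS is 72% against 64%, so HR = ln(0.64)/ln(0.72) = 1.36. With 100 deaths the drift is ln(1.36) × √(100/4) = 1.53. The chance of a nominally significant OS result favouring laparoscopy is Φ(−1.96 − 1.53), about 0.0002. It is not materially raised.

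**6. What a stricter rule costs if laparoscopy is truly worse.** Take the mortality HR of 1.65 from the retrospective cohort described in the Background (2.2.1, Surgical treatment), with 102 deaths. The drift is ln(1.65) × √(102/4) = 2.53. The chance of an OS harm signal is about 72% at 0.05. With the O'Brien-Fleming boundary it is about 34% at t = 0.45 and about 11% at t = 0.27.

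**The case against.** The sections can be read together: 5.3.3 d) supplies the method and 7.2 says who may act on it. Section 7.2 grants a right and imposes no duty to stop. The blanket 0.05 sentence is generic, and 5.3.3 d) already departs from it for the final analysis. Section 5.3.1 calls its methods an overview, with a detailed SAP to follow that could set the threshold. A sensitive trigger for harm is also defensible, given the earlier results that the protocol itself reports.

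Much of this stands. The step 2 figures are conditional on the 0.05 reading, and they are probabilities that the criterion is met, which need not lead to a stop. Step 6 shows that demanding O'Brien-Fleming evidence for harm has a real price. But no text links 7.2 to the O'Brien-Fleming boundary, and even the joint reading leaves PFS as a second trigger with no allowance of its own. If a clinically important difference was meant, the criterion is wholly undefined. A later SAP could settle the matter, but the clause as it stands is already a stated stopping criterion.

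Two stronger inferences are not supported. A reader might take the clause to be tested at every half-yearly committee meeting, with the chance of a false stop accumulating over many looks. The only twice-yearly schedule is in 8.2, and it is for the TSC's review of safety data; nothing says the ethics committee tests PFS or OS on that timetable. A reader might also infer that the 0.048 no longer means anything. Step 5 shows that the error that matters most in a non-inferiority trial is not materially affected.

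**Conclusion.** The concern holds as a conflict between two stated interim provisions and should be corrected. With truly equal arms and one look, the 7.2 criterion read at two-sided 0.05 is met by chance in 5% of trials on OS alone and about 7-9% on OS or PFS (ρ 0.9 to 0.5). O'Brien-Fleming at half information gives 0.5%, and less if the look comes earlier, as step 4 suggests. If 7.2 silently means the O'Brien-Fleming boundary for both endpoints, the excess is at most about two-fold.

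The size therefore depends on what significant means, which the documents do not say; ρ and t are also assumed. The consequence is a possible chance-driven stop that leaves 5-year OS unanswered.

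**What to change.** Reconcile 5.3.3 d) and 7.2.

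- **5.3.3 d)**: state that the interim look is on OS, with its planned information fraction and the O'Brien-Fleming boundary. At half information this is p of about 0.005, consistent with the final 0.048; at another fraction both levels need recalculating.
- **7.2**: define significant as crossing that boundary. Say which independent committee (DMC or TSC) sees the comparison and makes the recommendation on which the ethics committee acts.
- **PFS**: give it its own pre-specified boundary, or label it supportive and non-binding.
- **Harm**: if a more sensitive trigger is wanted, state it separately as a pre-specified, one-directional guideline.
- Keep the ethics committee's right to stop for ethical violations.

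The cost is a short amendment, with no extra patients or data. The ethics committee would no longer act on an unadjusted comparison. Unless a harm guideline is kept, a stop for harm would need stronger evidence, as step 6 shows. That trade-off should be decided openly.

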7.3 Quality Control

The study process will be closely followed by the project sponsor, the sub PIs of each study center, the CRO manager, and the surgical team. Data quality is monitored by the independent DMC, CRO project manager, and the surgical team.

Clinical observation and follow-up: surgical treatment plan, surgery-related indicators, intraoperative and postoperative complications, postoperative pathology records, postoperative adjuvant treatment including radiotherapy and chemotherapy dose and time, number of courses and adverse reactions; follow-up will be conducted every three months for 2 years after surgery; then every 6 months from year 3 to year 5 after surgery.

Measures to ensure patients' compliance: patients participating in this study will be given priority in our hospital for treatment, and post-operative follow-up will also be

assigned.

VIII. Definition and treatment of adverse events

8.1 Definition of adverse events

The Adverse Event (AE) is an adverse medical event that occurs after a patient or a subject in a clinical trial receives a drug, but is not necessarily causally related to the treatment.

Any adverse medical event that occurs in this trial from the time the patient signs the informed consent and receives the treatment until 1 month after the end of the treatment, regardless of whether it is causally related to the surgery performed, is judged as an adverse event, including symptoms, signs, diagnosis, and abnormal laboratory tests.

8.2 Observation, recording and treatment of adverse events

Observation and recording: the investigator should carefully observe any adverse events occurring in the patient during the study, and require the patient to truthfully reflect the changes in condition after treatment and avoid eliciting questions. Pay attention to adverse reactions or unanticipated toxicities (including symptoms, signs and laboratory tests) while observing side effects. Regardless of whether the adverse event is related to the surgery performed, it should be recorded in detail in the CRF, including the time of occurrence of the adverse reaction, symptoms, signs, extent, duration, laboratory test indicators, treatment methods, process, results, follow-up time, etc. The combined use of drugs should be recorded in detail for analysis of adverse event and test drug correlation, and the record should be signed and dated.

Medical treatment of patients: When adverse reactions are reported, the investigator should take necessary treatment measures according to the condition, such as dose adjustment, temporary interruption of medication, etc., and decide whether to terminate the trial. The occurrence of serious adverse events, the unit undertaking the pilot study must immediately take the necessary measures to ensure the protection of the safety of the subject.

The first safety analysis will be conducted after 20 patients have completed treatment. TSC will review all safety data collected during the study twice a year.

IX. Cost-benefit Analysis

We will also assess the subjects' household income and sources of surgical treatment costs, record their health insurance reimbursement rates, and evaluate the impact of different health insurance rates on patients' household burden.

X. Review

The main center at the Obstetrics and Gynecology Hospital of Fudan University will closely monitor the study. The monitor will maintain an effective understanding of the

study through observation, review of study records and source documents, and discussions with investigators and staffs about the conduct of the study. The main center or its designee will carefully monitor all aspects of the study to ensure that the study complies with applicable government regulations regarding current good clinical practice and current standard operating procedures.

Investigators and institutions involved in the study will allow trial-related monitoring, review, Institutional Review Board (IRB) or Human Research Ethics Committee (HREC) reviews and regulatory inspections through direct access to raw data/documents.

XI. Ethics and Dissemination

11.1 Ethical approval

A total of 1104 patients will be recruited in six centers: Obstetrics and Gynecology Hospital of Fudan University, Zhongshan Hospital affiliated to Fudan University, Xinhua Hospital affiliated to Shanghai Jiao Tong University School of Medicine, Renji Hospital affiliated to Shanghai Jiao Tong University School of Medicine, Taizhou Hospital Affiliated Cancer Hospital of the University of Chinese Academy of Sciences, and the First Affiliated Hospital of Wenzhou Medical University. All patients will be fully informed of the purpose, methods, benefits and potential risks of this clinical trial and sign the informed consent form.

The study protocol has been sent to each sub-center and has been reviewed and approved by the ethics committees of respective hospitals.

11.2 Study protocol modification plan

The main objective of this study is to observe PFS and OS after cervical cancer surgery. The patient sample size is large and the enrollment time is long, so it needs to take more than 3 years to complete the enrollment. Major surgery, postoperative treatment and initial follow-up could be completed during this period. It is expected that initial outcomes can begin to be produced after 3 years. However, tumor follow-up will require at least 5 years to obtain complete and comprehensive data, especially for PFS and OS. Previous similar studies have taken about 10 years to reach a final and convincing conclusion. After the initial 3 years of funding for this study, there is still numerous and long-term workloads that need to be completed. As a result, it is expected that regular follow-up and analysis will be needed for several years after the current grant ends. Therefore, we hope that the time frame for the use of funds and the time frame for the publication of results can be extended to facilitate the long-term implementation of the project and the final interpretation of the research results. If the project does not complete the study objectives or the task acceptance conclusion is false, the project lead organizations should return the outstanding funds.

